All required data collection for the project will be described below with timelines, data sharing procedures, and contact information in case there are issues. For any data collection challenges, please contact Project Coordinator [name] – [contact] or [contact]. For clinical guidance, adverse reactions, or concerns about subject safety, reach out to Principal Investigator, [name]. For non-emergencies, email – [contact] -or- [contact]. For urgent matters, [name] may be reached at [contact].

All SHARE Program Counseling Data Collection Tools for Treatment Group Cases are listed below:

Post-Session Case Notes:

Electronic Case Files: Throughout your sessions, you are expected to take detailed notes in the electronic case file provided to you in your Microsoft Teams channel for each assigned case. You will upload the completed version into the Teams folder for each session within **48 hours** of completion. The electronic case file includes each of the following sections, per session:

- **Session Preparation:** A list of what tools you will need to have reviewed and/or ready prior to that session.
- **Changes Since Last Session:** Here you will report any major changes that either care partner has experienced since the last time you spoke with/met them. This is an important reporting requirement to our funder. If anything, major has occurred, please fill out an **Adverse Event Form** as soon as possible and send it as an encrypted file to [contact] within 24 hours -or- upload it to your Teams Channel.
- **Session Information:** Basic information about the session [date, time of session, session duration, PWD location, CG location).
- **Session Counselor Evaluation:** Each treatment session will include an evaluation of session components from your perspective.
- **Readiness Ratings:** You will rate each care partner's level of readiness at the end of each session and note any important contents to support your rating in the box provided.
- **Session Notes:** Complete notes on your session at the of the case file for that session.

Procedures:

- **Electronic Case File:** Save the document after each completed session and name the most recent case file into the Completed Data Folder for your case using the following convention:
 - #####_Session1_Case File Complete
 - #####_Session2_Case File Complete
 - #####_Session3_Case File Complete
 - #####_Session4_Case File Complete
 - #####_FamilySession_Case File Complete

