13.1 Specification of Safety Parameters

Safety parameters for the control condition will be assessed after each single session is completed, by clinical assessment. For experimental session (SHARE), safety parameters will be assessed after each session, also by clinical assessment. Criteria for concern includes adverse behavioral changes, significant change in diagnosis or prognosis, and suicidal ideation. If a participant reports changes at the start of a session, the SHARE Counselor will immediately notify the study team, and programming will either resume or stop, depending upon the nature of the report. If information is shared that falls within the identified criteria for concern at any point, the SHARE Counselor will be instructed to contact the study PI immediately for guidance. If this occurs at a clinical level that then results in an AE it will be reported to the DSMC and IRB.

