13.4 Severity of Event

All AEs will be assessed by a qualified medical professional. Events will be graded using the criteria below. Since this is a non-medical study, no toxicity tables or like criteria can be utilized.

For adverse events (AEs) the following guidelines will be used to describe severity.

Mild – Events require minimal or no treatment and do not interfere with the participant's daily activities.

Moderate – Events result in a low level of inconvenience or concern with the therapeutic measures. Moderate events may cause some interference with functioning.

Severe – Events interrupt a participant's usual daily activity and may require systemic drug therapy or other treatment. Severe events are usually potentially life-threatening or incapacitating. Of note, the term "severe" does not necessarily equate to "serious."

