13.6 Follow-up for Adverse Events

The occurrence of an adverse event (AE) or serious adverse event (SAE) may come to the attention of study personnel during study visits and interviews of a study participant presenting for medical care, or upon review by a study monitor.

All AEs including local and systemic reactions not meeting the criteria for SAEs will be captured on the appropriate case report form (CRF). Information to be collected includes event description, time of onset, qualified medical professional's assessment of severity, relationship to study product (assessed only by those with the training and authority to make a diagnosis), and time of resolution/stabilization of the event. All AEs occurring while on study must be documented appropriately regardless of relationship. All AEs will be followed to adequate resolution.

Any medical condition that is present at the time that the participant is screened will be considered as baseline and not reported as an AE. However, if the study participant's condition deteriorates at any time during the study, it will be recorded as an AE.

Changes in the severity of an AE will be documented to allow an assessment of the duration of the event at each level of severity to be performed. AEs characterized as intermittent require documentation of onset and duration of each episode.

The PI will record all reportable events with start dates occurring any time after informed consent is obtained until 7 (for non-serious AEs) or 30 days (for SAEs) after the last day of study participation. At each study visit, the investigator will inquire about the occurrence of AE/SAEs since the last visit. Events will be followed for outcome information until resolution or stabilization.

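### The counselor instructions trigger an Adverse Event Form only for undefined major changes, while 13.2 and 13.6 require every AE to be documented, so mild or moderate AEs can be left without a form

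*Protocol*

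**What the plan says.** The counselor procedures printed under Protocol 9.0 describe the electronic case file for treatment cases. Its section on changes since the last session instructs: "Here you will report any major changes that either care partner has experienced since the last time you spoke with/met them". The form for adverse events is requested under a similar condition: "If anything, major has occurred, please fill out an". On timing and route, the counselor is to complete it promptly and choose between an encrypted file and an upload: "within 24 hours -or- upload it to your Teams Channel". At the head of the same treatment procedures is a general line: "For clinical guidance, adverse reactions, or concerns about subject safety, reach out to Principal Investigator".

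The safety sections are wider:

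- 13.2 defines an AE as any untoward medical occurrence during participation, related or not, with no severity threshold.
- 13.4 grades AEs as mild, moderate or severe. Mild is described as: "Events require minimal or no treatment and do not interfere with the participant's daily activities".
- 13.6 sends non-serious AEs to a case report form, counts deterioration of a baseline condition as an AE, and adds: "All AEs occurring while on study must be documented appropriately regardless of relationship".
- 13.1 sets a notice rule for counselors: "If a participant reports changes at the start of a session, the SHARE Counselor will immediately notify the study team". It also requires immediate contact with the Principal Investigator when one of its criteria for concern is met.

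**The concern.** The page the counselor works from uses a narrower test than the sections that define and require AE recording. *Major* is left to the judgment of the individual counselor, and 5.1 expects counselors to differ in prior training and experience. Two counselors hearing of the same minor fall or brief illness could act differently, and both would be following their instructions.

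At stake is the completeness of the AE record. The quarterly safety reports (13.2 and 17.1) are to analyze AEs as well as SAEs, and any later statement that the adapted program is low risk will rest on that record. If the regular session contact filters out the lower grades, the count is incomplete by the protocol's own standard, and by an amount nobody can recover afterwards.

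**Working it through.** There is no stated figure to reproduce. The check sets the passages side by side.

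| Question | Counselor instructions (9.0, Treatment) | Safety sections |
|---|---|---|
| What is to be reported? | Major changes | All AEs (13.6), as defined in 13.2 |
| Is the threshold defined? | No | No threshold; three grades, mild included (13.4) |
| Does relatedness matter? | Not addressed | No (13.2, 13.6) |
| What opens a form? | Something major has occurred | Every AE goes on a case report form (13.6) |

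**Step 1. Can an AE fall below the trigger?** Yes. A mild event under 13.4 needs little or no treatment and leaves daily activities unaffected. On any ordinary reading it is not major, yet it is an AE. The same holds for a modest worsening of a baseline condition, which 13.6 makes an AE and which is to be expected in people with dementia. Some moderate events, involving limited inconvenience or interference, may also fall below.

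**Step 2. Does another route catch what the form misses?** Four routes exist, and each is partial.

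- *Contact with the Principal Investigator* (9.0): not limited to major events, but worded for adverse reactions and safety concerns, with no form or deadline. An unrelated minor illness need not prompt it.
- *Assessment after each session* (13.1): the criteria for concern are adverse behavioral change, significant change in diagnosis or prognosis, and suicidal ideation. These are narrower than the AE definition.
- *Investigator inquiry at each study visit* (13.6): this covers all AEs, but the sessions are run by counselors, and the schedules in 8.0 contain no AE row.
- *Researcher call after each session* (9.0): asks about the family's experiences; no AE question is stated.

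**Step 3. How much contact does the instruction govern?** Inputs: 60 treatment dyads (7.0) and 5 to 6 case files per completed case, since the family session is optional (9.0, Treatment).

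- Sessions if all are completed: 5 × 60 = 300 to 6 × 60 = 360.
- People: 2 × 60 = 120.
- These are ceilings. Section 5.2 allows for 20% attrition. Assuming it falls evenly on the arms, 0.20 × 60 = 12 dyads; if none of those attended a session, 5 × 48 = 240 sessions would remain.

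This counts occasions on which the narrower test applies. It does not count missed events.

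**Step 4. Timing.** The form is to be completed as soon as possible, and 24 hours is attached to the encrypted file; the alternative is joined on: "within 24 hours -or- upload it to your Teams Channel". The text does not say outright whether the limit covers both routes. Because 13.3 starts the investigator's 48 hours at occurrence, it is worth stating.

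**The case against.** The best defense is that this is a loose word in one bullet and that the form is not the only way an event reaches the investigator. Section 13.6 puts the recording duty on the Principal Investigator. Section 13.2 says all subject data are reviewed regularly, and counselors must keep detailed session notes and upload them within 48 hours. An event not called major may well be seen in those notes. This stands as far as it goes: it rules out saying that events *will* be lost. It does not remove the contradiction, because the notes have no AE prompt below the major level and the other routes are partial.

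A reader might also infer several stronger points that the documents do not support:

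- *That 13.1 requires immediate notice of every AE.* It covers changes reported at the start of a session and the criteria for concern. The rule about every AE is the recording rule in 13.6.
- *That the notice and form rules conflict.* Immediate notice followed by a form satisfies both.
- *That the Teams upload has no deadline at all.* The instruction to act as soon as possible precedes both routes, 24 hours can be read as covering both, and 13.3 says the form carries its own reporting timeline. The form is not shown.
- *That counselors are untrained in AE reporting.* The form is absent from one webinar's list of materials, but that webinar follows an online course and human subjects training whose contents are not shown.
- *That a given share of AEs would be lost.* No AE rate or severity mix is given, so any percentage would be an assumption.
- *That ascertainment differs by arm.* The control instructions contain no matching text on changes or the form, but the contents of the control case file are not described and 13.1 applies safety assessment to the control session too.

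**Conclusion.** The inconsistency is real and specific. The form's trigger in the treatment counselor instructions is undefined and narrower than 13.2, 13.4 and 13.6. A counselor who complies with it can leave mild, and some moderate, AEs without a form. The conclusion rests on reading *major* in its ordinary sense, as the protocol gives no other.

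The number of events affected cannot be estimated from the documents. The other routes reduce it by an unknown amount. The timing wording needs clarifying but is not a contradiction in itself. This should be corrected because the correction is cheap and the omission cannot be repaired after the fact; it does not put the trial's design in question.

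**What to change.** Reconcile the bullet on changes since the last session with 13.2 and 13.6:

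1. Replace *major* in both places with a reference to the protocol's own definition: the form is completed for any occurrence that meets the AE definition in 13.2, including deterioration of a baseline condition as described in 13.6, whatever its severity or apparent relationship.
2. State that the 24-hour limit applies to both the encrypted-file and the Teams-upload routes.
3. State that the form is in addition to, and not a substitute for, the immediate notice in 13.1.

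The cost is the rewording of one bullet and a notice of the change to counselors. The downside is more forms, mostly for mild events, although 13.6 already requires those events to be documented.

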****This concludes your treatment case****

DATA COLLECTION PROCEDURES

Control

All SHARE Program Counseling Data Collection Tools for Control Group Cases are listed below:

Post-Session Case Notes:

Throughout your session, you are expected to take detailed notes in the control group electronic case provided to you in your Microsoft Teams channel for each assigned control case. You will upload the completed version into the Teams folder Completed Data for that case within **48 hours** of completion of the session, following these procedures.

Procedures:

- **Electronic Case File:** Save the document after your completed control group session into the Completed Data Folder for your case using the following convention:
 - #####_ControlSession_Case File Complete
- **Other Fillable Data Forms:**
 - **Control Group Handout:** We will provide the Control Group Handout in the Resources folder within a Control Group Materials subfolder in your Teams Channel for each case. You will use this blank document to conduct the Control Group session with your assigned control care partners.

Data Collection Milestones:

At the end of your control session, the following data elements are due in your Microsoft Teams Channel folder in the Completed Data folder within **48 hours** of your session ending:

Session 1:

- Completed Control Group Electronic Case file
- Completed Control Group Handout

Post Session Email:

- Once you are completed with your control case, within 48 hours you will email [contact] that your case is complete and all of your data have been collected.

Evaluations of Your Care Partners:

- At the end of your control session, a researcher will call the family on the phone and will ask them questions about their experience. Please remind the family at the end of the session that someone from Benjamin Rose is going to call them to check in. This call will take place within 48 hours within your data being received in the Teams folder, confirming the session took place.

THIS SECTION PURPOSEFULLY LEFT BLANK

PLEASE CONTINUE TO THE NEXT PAGE

11.0 FOLLOW-UP

The intervention period in this low-risk study of a non-pharmacological intervention is just three months in length. As such, follow up is not required. The final point of contact for all dyads will be the post-treatment assessment / interview. Upon completion of the study, there will be no follow-up required.

12.0 EARLY DISCONTINUATION

Participants are free to withdraw from participation in the study at any time and for any reason.

13.0 SAFETY REPORTING

[name] and [name] (PI and Consultant) will be responsible for ensuring participants' safety on a daily basis during their participation in Aim 4. Data and safety monitoring will be assured by the study's Research Team Senior key personnel: The PI and study consultants, [name] and [name], are experts in the field of dementia/chronic illness and dyadic research. Along with [name], they will make up the study's Data and Safety Monitoring Committee (DSMC). This team will act to monitor participant safety, evaluate the progress of the study, review procedures for maintaining the confidentiality of data, the quality of data collection, management, and analyses.

[name], [name], and [name] will be informed of any serious adverse events as soon as they occur and will notify the Institutional Review Board of record within 24 hours of notification. The DSMC will meet quarterly with members of the research team either in-person or by teleconference to review the study's progress, review data quality, and participants' safety. At these meetings, an evaluation of the progress of the study will be reviewed, including periodic assessments of data quality, timeliness of recruitment, the appropriateness of the strategies for recruiting participants into the study, assessing the participants' risk in using SHARE materials, and other factors that might affect the study's outcomes.

In the event of an adverse reaction, the DSMC will meet within 24 hours and the following information will be reviewed:

- Participant's study status
- How the participant was recruited into the study and the efforts that took place to retain him/her.
- The nature of the adverse reaction and a determination of how the participant's safety has been threatened as a result.
- A recommendation for how to treat the adverse reaction. In most cases, a recommendation would be to discontinue the individual's participation in the intervention and/or to withdraw the participant from the study. In more severe cases, the participant might be referred to an identified expert (the Alzheimer's Association, a geriatric care manager or licensed clinical social worker, etc.).
- If the adverse reaction is deemed to be very serious (i.e., suicidal risk or the health/well-being of the participant is in jeopardy), the case will be reported to the appropriate authorities to intervene on the situation immediately.
- Any significant adverse reactions will be reported to the IRB within 24 hours of notification.

For the purposes of this study, a participant is considered enrolled if they have successfully completed the screening procedure outlined above. This study will be monitored by the DSMC specified above.

After being enrolled in the study, participant safety will be monitored regularly by the PI with reports being sent to the DSMC quarterly, in advance of the meetings.

As this is a minimal risk psychosocial activity intervention no AEs or SAEs are expected per NIH definitions, as it is unlikely that the risks of the study will affect medical outcomes or occurrences. However, if any AEs do occur, whether they appear study-related or not, they will be reported to the DSMC and the IRB within 48 hours of occurrence. Any deaths to study participants, from whatever cause, will be reported within 24 hours. The DSMC and IRB will then make the determination of whether they should be reported to the NIA.

If any AEs or SAEs occur, the PI will, with the assistance of the DSMC, determine if any modifications need to be made to the study protocol and procedures.

13.1 Specification of Safety Parameters

Safety parameters for the control condition will be assessed after each single session is completed, by clinical assessment. For experimental session (SHARE), safety parameters will be assessed after each session, also by clinical assessment. Criteria for concern includes adverse behavioral changes, significant change in diagnosis or prognosis, and suicidal ideation. If a participant reports changes at the start of a session, the SHARE Counselor will immediately notify the study team, and programming will either resume or stop, depending upon the nature of the report. If information is shared that falls within the identified criteria for concern at any point, the SHARE Counselor will be instructed to contact the study PI immediately for guidance. If this occurs at a clinical level that then results in an AE it will be reported to the DSMC and IRB.

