8.0 STUDY MEASUREMENTS AND PROCEDURES

See section 3.0 Study Flow for details on study procedures between screening and study completion. The below tables document the study timeline and schedule divided between PWD and CG study protocols.

PWD Timeline and Schedule				
Interview/Data Collection	Screening (1 week)	Baseline (within 2 weeks after screening)	Treatment or Control Period (Tx; 8-10 weeks; C: single session)	Follow-Up (within 2 weeks of completion of intervention period)
Informed Consent Form	X			
Confirm Age 50+ (Screening)	X			

Confirm Read & Speak English (Screening)	X			
Confirm Dementia Symptoms or Diagnosis (Montreal Cognitive Assessment; MOCA)	X			
Confirm Exclusion Criteria Do Not Apply	X			
Enrollment (if eligible)	X			
Service Availability Measure (SAM)		X		X
Care Values Scale		X		X
Preferences for Care Tasks Scale		X		X
Dyadic Relationship Scale (DRS)		X		X
Personal and Instrumental Activities of Daily Living (PADL & IADL)		X		X
Emotional-Intimacy Disruptive Behavior Scale (EIDBS)		X		X
Dementia Quality of Life +/- Affect		X		X
Center for Epidemiological Studies Depression Scale (CES-D)		X		X
Leisure & Healthy Behaviors		X		X
Quality of Life – AD (QoL-AD)		X		X
SHARE Care Plan (Treatment ONLY)			X	
Resource List (Control ONLY)			X	
Post-Session Evaluation (1 – Control; up to 6 – Treatment)			X	
Treatment Fidelity / Acceptability Measures			X	
Satisfaction Questions				X

CG Timeline and Schedule				
Interview/Data Collection	Screening (1 week)	Baseline (within 2 weeks after screening)	Treatment or Control Period (Tx; 8-10 weeks; C: single session)	Follow-Up (within 2 weeks of completion of intervention period)
Informed Consent Form	X			
Confirm Age 50+	X			

(Screening)				
Confirm Read & Speak English (Screening)	X			
Confirm Dementia Symptoms or Diagnosis (Dementia Rating Scale)	X			
Confirm Exclusion Criteria Do Not Apply	X			
Enrollment (if eligible)	X			
Service Availability Measure (SAM)		X		X
Care Values Scale		X		X
Preferences for Care Tasks Scale		X		X
Dyadic Relationship Scale (DRS)		X		X
Personal and Instrumental Activities of Daily Living (PADL & IADL)		X		X
Personal and Instrumental Activities of Daily Living (PADL & IADL)		X		X
Emotional-Intimacy Disruptive Behavior Scale (EIDBS)		X		X
Dementia Quality of Life +/- Affect		X		X
Center for Epidemiological Studies Depression Scale (CES-D)		X		X
Stress in Providing Care		X		X
Leisure & Healthy Behaviors		X		X
Quality of Life – AD (QoL-AD)		X		X

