 - #####_Session5_Case File Complete

At the completion of all sessions, your case should have 5-6 completed case files (5 if there is no family session held).

*You will **NEVER** share the Electronic Case File with the family. This is a research document **ONLY**.

- **Other Fillable Data Forms:**

[You will email these to families using encryption as often as you'd like]

- **Care Values:** We will provide an initial Care Values Comparison document in a Care Values folder for you in your Teams Channel for each case. You will use this document to conduct the Care Values Discussion in Session 1.
- **SHARE Care Circles:** We will provide you with three SHARE Care Circles documents for you in a Care Circles folder in your Teams Channel for each case. Two files will be there for you: PWD's Care Circles and CG's Perceptions Care Circles. You will use then use the PWD's document to conduct the Care Preferences discussions in Session 2. You will resave that document into a new version that will contain the final Care Circles. You will name that document beginning with the ID#: #####_CareCircles_Session2_FINAL.

Data Collection Milestones:

At the end of each session, the following data elements are due in your Microsoft Teams Channel folder in the Completed Data folder within **48 hours** of your session ending:

Session 1:

- Electronic Case file
- Revised Care Values file (if care values were adjusted in Session 1)

Session 2:

- Electronic Case file
- Revised Care Values file (if care values were adjusted in Session 2)
- Revised Care Circles file (demonstrating the new SHARE Care Circles)

Session 3:

- Electronic Case file
- Completed SHARE Care Plan created in Session 3
- Revised Care Values file (if care values were adjusted in Session 3)
- Revised Care Circles file (if care preferences were adjusted in Session 3)

Session 4:

- Electronic Case file
- Completed Family Session Agenda [Counselor Version; the Family version you will send to the family]
- Revised SHARE Care Plan (if Plan changed after having Session 4 discussions)
- Revised Care Values file (if care values were adjusted in Session 4)
- Revised Care Circles file (if care preferences were adjusted in Session 4)

Family Session:

- Electronic Case file
- Revised SHARE Care Plan (if Plan changed after Family Session)
- Revised Care Values file (if care values were adjusted in Family Session)
- Revised Care Circles file (if care preferences were adjusted in Family Session)

Session 5:

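### Safety checks tied to sessions occur once in control and five or six times in SHARE, over windows of different length, so raw adverse event counts by arm are not like for like

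*Protocol*

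**What the plan says.** Section 13.1 sets the safety check by arm. For control: "Safety parameters for the control condition will be assessed after each single session is completed, by clinical assessment". For SHARE: "For experimental session (SHARE), safety parameters will be assessed after each session, also by clinical assessment". The counselor procedures for treatment cases give the number of sessions: "your case should have 5-6 completed case files (5 if there is no family session held"). The evaluation calls follow the same pattern in Section 8.0: "Post-Session Evaluation (1 – Control; up to 6 – Treatment").

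The treatment case file has a section on changes between sessions: "Here you will report any major changes that either care partner has experienced since the last time you spoke with/met them". A major change triggers an Adverse Event Form within 24 hours. The matching control procedures ask for notes, a case file and a handout, and mention neither step.

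On duration, Section 8.0 heads the column "Treatment or Control Period (Tx; 8-10 weeks; C: single session") and times the last interview as "Follow-Up (within 2 weeks of completion of intervention period"). Section 11.0 gives a three-month intervention period without separating the arms and adds: "The final point of contact for all dyads will be the post-treatment assessment / interview".

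Section 13.6 applies to everyone. It requires enquiry about adverse and serious adverse events at each study visit, looking back to the previous one. Events are recorded from consent until 7 days (non-serious) or 30 days (serious) after last participation. Section 13.2 sends the Data and Safety Monitoring Committee (DSMC) a quarterly analysis of these events.

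**The concern.** Two things differ between the arms by design: how often someone is in a position to hear of an event, and for how long. Adverse events here include any untoward medical occurrence, related or not, so background illness in older people with dementia and their caregivers counts. With more contacts and more weeks, the SHARE arm will tend to show more events even if SHARE does no harm.

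What is at stake is how the safety data are read. The DSMC is asked in Section 13.0 to assess the risk of using SHARE materials and to help decide on protocol changes if events occur. The control arm could show which events are background, but only if events are sought in the same way there. A later analysis plan can adjust for time at risk. It cannot recover events that nobody asked about.

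**Working it through.** **Session count.** The listed case files are Sessions 1 to 4, the Family Session and Session 5: 6 files, or 5 without the Family Session. This reproduces the protocol's figure of 5-6.

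**Contacts at which safety is assessed.**

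| Contacts counted | SHARE | Control | Ratio |
|---|---|---|---|
| Section 13.1 check only | 5-6 | 1 | 5-6 |
| Plus follow-up interview (Section 13.6) | 6-7 | 2 | 3.0-3.5 |
| Plus baseline interview | 7-8 | 3 | 2.3-2.7 |

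**First session to follow-up, at the 2-week limit.** SHARE: 8 + 2 = 10 to 10 + 2 = 12 weeks. Control, timed from its single session: 0 + 2 = 2 weeks. Ratio 5 to 6.

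**Full recording window.** Inputs:
- screening 1 week and baseline 0-2 weeks later (Section 8.0);
- 0-2 weeks to the first session. The Case Scheduling text returns a case not scheduled within two weeks; I assume the session falls within that time;
- treatment period 8-10 weeks in SHARE, taken as 0 in control (Section 8.0);
- follow-up 0-2 weeks later (Section 8.0);
- a tail of 7 days = 1 week, or 30 days = 30/7 = 4.29 weeks (Section 13.6).

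Control window = screening + baseline gap + scheduling gap + follow-up gap + tail. SHARE window = the same sum + 8 to 10. The gaps are assumed equal in the two arms.

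| Tail | Gaps | Control (weeks) | SHARE (weeks) | Ratio |
|---|---|---|---|---|
| 7 days | all 0 | 1 + 1 = 2 | 10-12 | 5.0-6.0 |
| 7 days | all 2 | 1 + 6 + 1 = 8 | 16-18 | 2.0-2.25 |
| 30 days | all 0 | 1 + 4.29 = 5.29 | 13.29-15.29 | 2.5-2.9 |
| 30 days | all 2 | 1 + 6 + 4.29 = 11.29 | 19.29-21.29 | 1.7-1.9 |

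**Illustration in events.** The protocol gives no event rate, so I assume one that is equal in both arms. Expected events = 60 dyads × rate per dyad-week × weeks. With windows of 18 and 8 weeks:
- rate 0.01: 10.8 versus 4.8;
- rate 0.02: 21.6 versus 9.6;
- rate 0.05: 54 versus 24.

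The rate cancels from the ratio (18/8 = 2.25 throughout). These figures reflect window length only; contact frequency would add to the gap.

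**Does Section 13.6 remove the difference?** Not fully.
- Its window ends relative to last participation, so the extra 8-10 weeks remain in SHARE.
- It adds the same number of visits to each arm, which narrows the contact ratio but does not close it.
- The enquiry is not carried into the working documents. Neither arm's schedule in Section 8.0, nor the follow-up list in Section 15.0, has an adverse event item.
- The 7- and 30-day tails fall after what Section 11.0 calls the last contact, so no scheduled contact covers them.

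**The case against.** The strongest reply is that a reader might infer that control dyads are assessed for safety only once and that their harms go unseen. The text does not support that. Section 13.6 makes no distinction by arm, both arms have a follow-up interview, and Section 13.1 tells counselors in either arm to contact the principal investigator if a criterion for concern arises. The control case file's contents are not listed, so it may already have a field for changes. All of this stands, and it limits the point to unequal ascertainment and a gap between Section 13.6 and the forms.

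A reader might also infer that events cannot be compared between arms at all, or that the protocol plans a biased comparison. Neither follows. Deaths and other serious events depend less on how often people are asked, and rates per person-time or a common window allow a usable summary. The protocol states no between-arm comparison of events; relative safety is not an aim, and individual events are judged for severity and relatedness. That the DSMC would act on a count imbalance is a possibility, not something the document says.

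Finally, a fixed threefold excess is not established. It depends on which gaps and tail are counted and on when control follow-up takes place. If control follow-up were held at the same time after baseline as in SHARE, the windows would match. Only the contact difference (2 versus 6-7 with follow-up counted) would remain. Section 8.0 points to a control follow-up within 2 weeks of the single session, while Section 11.0 leaves it open.

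**Conclusion.** The point holds in a limited form. Safety checks linked to sessions run at 5-6 to 1, or 3.0-3.5 to 1 once the follow-up interview is counted. If control follow-up is timed from the single session, the recording window is about 2 to 6 times longer in SHARE for non-serious events and about 1.7 to 2.9 times longer for serious ones. Raw counts by arm would therefore tend to be higher in SHARE with equal true rates. The direction does not depend on the assumed event rate, but the size depends on equal gaps in both arms and on the control follow-up date.

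In a study described as minimal risk, with no stated between-arm safety analysis, this is a modest defect. It is worth correcting because the correction is cheap and has to be made in data collection rather than in analysis.

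**What to change.** 1. Put the Section 13.6 enquiry into the follow-up interview of both arms as one identical scripted set of adverse and serious adverse event questions with a defined look-back. It should be asked whether or not an event was already reported at a session. List it in the Section 8.0 schedules and the Section 15.0 follow-up forms.
2. Add the change report and Adverse Event Form step to the control data collection procedures.
3. State in Section 13.2 that any by-arm summary rests on the follow-up enquiry, either with person-time or restricted to a window common to both arms. Section 13.6 already collects time of onset, so the restriction is feasible. Report session-detected events separately, as descriptive.
4. Reconcile Sections 8.0, 11.0, 13.1 and 13.6 on when control follow-up and adverse event enquiry take place.

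The cost is a few more questions in an existing telephone interview, plus wording. The control follow-up need not move; moving it would change when every outcome is measured in that arm and is a separate decision.

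Some imbalance will remain. Person-time corrects for duration, on the assumption of a roughly constant rate, but does not remove all of the difference in contact frequency. A common early window asks SHARE dyads to recall events from further back.
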